Cohort 2 will only be initiated after review of safety data from Cohort 1. Thereafter, Cohort 3 will be initiated after review of safety data from Cohort 2. Cohorts 4 and 5 will be initiated after review of safety and PK data from their respective single-dose cohorts. An additional requirement for Cohort 5 is confirmation that at least 2 patients have received at least 3 doses each of LY3002813 safely in Cohort 4. Cohort 6 and Cohort 7 may proceed in parallel with Cohorts 4 and 5, respectively. In addition, Cohort 7 will only be initiated after confirmation that at least 2 patients have received at least 2 doses each of LY3002813 safely in Cohort 6.

Safety/PK reviews will occur after a minimum of 4 patients receiving LY3002813 and 1 patient receiving placebo have been dosed. For Cohorts 1 to 3, no more than 1 patient will be dosed on any one particular day. For Cohorts 4 to 7, patients dosed on the same day at any one site should not be dosed simultaneously but should be separated by at least 1 hour. Each cohort will contain approximately 6 (single dose) or 9 (multiple dose) patients treated with LY3002813 and 2 to 3 patients treated with placebo so that the study can detect target engagement and ADA frequency relative to those observed in Study AACC.

The primary target engagement outcome is the reduction of cerebral amyloid as measured by quantitative amyloid PET imaging (florbetapir SUV_r) assessed at baseline and at 12 weeks, 24 weeks, 36 weeks, 48 weeks, and 72 weeks after starting treatment. The early postbaseline scans are aimed to assess the time course of amyloid reduction; the later scans are aimed to assess sustainability of amyloid reduction after completion of dosing in Parts A and B, and maximal amyloid removal in Part C.

Safety and PK of LY3002813 will be assessed throughout the study for each cohort. In addition, blood samples for the assessment of immunogenicity will be taken at regular intervals throughout the dosing and follow-up periods. For Cohorts 1 through 3, a CSF sample will be taken by single lumbar puncture (LP) at baseline, another approximately 3 days after dosing to measure the CSF concentration of LY3002813 and CSF biomarkers. For Cohorts 4 through 7, a CSF sample will be taken by single LP at baseline and after 24 weeks dosing, or the last dose if treatment is stopped earlier.

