11.2.5.1. Imaging Analyses

Statistical assessment of the SUVr will be analyzed by a mixed model repeated measure (MMRM). The planned analyses is an MMRM using at least compound symmetry covariance structure with fixed effects of treatment doses (LY3002813 and placebo), study visit, and interaction between treatment and visit. A baseline covariate adjustment may be used. The primary comparison is between LY3002813 and placebo for change from baseline in composite SUVr or percent change in composite SUVr at last PET imaging visit. This analysis may be repeated for SUVrs in individual brain regions if needed.

In addition to the MMRM analysis, a Bayesian posterior probability may be computed for each LY3002813 dose compared to placebo. For each dose, the credible interval will be computed for each dose relative to placebo.

Changes in volume (including, but not limited to, whole brain, ventricle, and hippocampus), brain tissue microstructure, and functional connectivity in brain networks captured by MRI over the course of the study will be explored; exploratory evaluation of whole brain and anatomically localized structural and functional changes will be summarized. MRI will be obtained every 12-24 weeks; therefore, an MMRM may be conducted fitting treatment and study visit as fixed effects.

Additionally, the relationship between LY3002813 serum exposure and imaging endpoints may be explored graphically or by a modeling approach.

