#### 3.4. Summary of Study Design

This study (Study I5T-MC-AACD [AACD]) will enroll patients with MCI due to AD, mild AD, or moderate AD with amyloid deposition confirmed by amyloid PET imaging using the National Institute on Aging-Alzheimer's Association (NIAAA) work group consensus guidelines (Albert et al. 2011, McKhann et al. 2011). This study will be conducted in multicountry sites including the United States and Japan. Up to 150 patients may be enrolled to ensure that approximately 72 patients (7 dosing cohorts of 8-12 patients) complete the study.

The study will be conducted in at least 7 cohorts ([Figure AACD.3.1](#)):

- Cohort 1: 10 mg/kg intravenous (IV) single dose
- Cohort 2: 20 mg/kg IV single dose

- Cohort 3: 40 mg/kg IV single dose (initiated after the 4-week safety review of Cohort 2)
- Cohort 4: 10 mg/kg IV every 2 weeks (Q2W) for 24 weeks
- Cohort 5: 20 mg/kg IV Q2W for 24 weeks (initiated after the 4-week safety review of Cohort 2; dosing interval may be modified based on single-dose PK of 20 mg/kg LY3002813)
- Cohort 6: 10 mg/kg IV every 4 weeks (Q4W) for up to 72 weeks
- Cohort 7: 20 mg/kg IV Q4W for up to 72 weeks (initiated after the 4-week safety review of Cohort 2)

[figure not shown]
Cohorts 1, 2, 4, and 6 may be initiated in parallel. Cohorts 3, 5, and 7 can only be initiated after a review of safety data from a minimum of 4 patients on LY3002813 and 1 patient on placebo completing the 4-week safety review in Cohort 2. Each cohort will contain 6 to 9 patients treated with LY3002813 and 2 to 3 patients treated with placebo so that the study can detect target engagement and ADA frequency relative to those observed in Study I5T-MC-AACC (AACC).

The primary target engagement outcome is the reduction of cerebral amyloid as measured by quantitative amyloid PET imaging (SUVr) assessed at baseline and 12 weeks, 24 weeks, 36 weeks, 48 weeks, and 72 weeks after starting treatment. The early postbaseline scans aim to assess the time course of amyloid reduction; the later scans aim to assess sustainability of amyloid reduction after completion of dosing in Parts A and B, and maximal amyloid removal in Part C.

[figure not shown]

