##### **4.2.5.1. Primary Objective of Amyvid PET Imaging Statistical Analyses**

Statistical assessment of the composite SUVr change from baseline will be analyzed by a mixed model repeated measure (MMRM). The response measurements are (1) SUVr change from baseline and (2) the percent change from baseline. Baseline is defined as the pre-dose SUVr obtained at screening visit 3 or prior to randomization. The change from baseline are computed from the SUVr obtained from the scheduled study visits at weeks 12, 24, 36, and 48. Patients have the option to have a PET image taken at early discontinuation. In those case, SUVr value will be mapped to the closest scheduled study visit at weeks 12, 24, 36, or 48. The planned analyses is an MMRM using an appropriate covariance structure with fixed effects of treatment doses (LY3002813 and placebo), study visit, and interaction between treatment and visit. A baseline covariate adjustment may be used. The primary comparison is between LY3002813 IV doses and placebo for change from baseline in composite SUVr or percent change in composite SUVr at last PET imaging visit. This analysis may be repeated for individual brain regions of SUVr if needed. A table of the LSmeans per dose group with associated p-value contrast to placebo will be constructed. A graphical summary of the LSmeans and a mean confidence interval on the y-axis and the study visit on the x-axis for each IV dose-group. Given the small sample size of n=6 patients per IV dose group, simplification of the mixed-effects model might be considered if the model fails to converge or other model fit diagnostics.

In addition to the MMRM analysis, a Bayesian posterior probability may be computed for each LY3002813 dose compared to placebo. For each dose, the credible interval will be computed for each dose relative to placebo. This analysis may be omitted if access to appropriate software such as SAS version 9.4 is not available.

Summary tables for SUVr values across the PET scan study visits for each IV dose group will include the n, mean, median, SD, minimum, maximum values. In addition, the number of patients within each IV dose group and study visit with post-dose composite SUVr values less than 1.2.

In addition to Amyvid PET scan SUVr analysis, an exploratory analysis of 18F-AV-1451 PET scan SUVr results will be conducted using an analysis of covariance (ANCOVA) model. The

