18F-AV-1451 PET scans will be obtained from each randomized patient at pre-dose Visit 4 and at Visit 17 approximately 72 weeks post-dose. The change in SUVr as the response variable and the IV dose group as the explanatory factor with the baseline SUVr as a covariate. The primary contrast will be the mean change in SUVr of each IV dose group relative to placebo. A summary table of the LSmean results and contrast p-value will be generated. In addition, a graphical display of the LSmean and confidence interval on the y-axis and the IV dose-groups and placebo along the x-axis.

Magnetic resonance imaging changes in volume over the course of the study will be explored, and exploratory evaluation of whole brain and anatomically localized structural changes will be summarized (including, but not limited to, whole brain, ventricle, and hippocampus). Magnetic resonance imaging volumetric assessments will be obtained at baseline, 24 weeks, 48 weeks, and 72 weeks as applicable. An MMRM will be constructed by fitting treatment and study visit as fixed effects. Response variables are brain structural changes of whole brain, ventricle, and hippocampal volumes.

Additionally, the relationship between LY3002813 serum exposure and imaging endpoints may be explored graphically or by additional exploratory analyzes.

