#### **4.2.5.2. Assessment of Cognitive and Functional Measurements**

Statistical assessment of the total cognitive measurement change from baseline will be analyzed by an MMRM. The response measurements are (1) change from baseline and (2) the percent change from baseline for ADAS-Cog (14), ADL, MMSE, FCSRT-IR total, CDR-Sum of Boxes, and NTB. Baseline for each measurement is defined as the pre-dose measurement obtained at screening Visit 3 or prior to randomization. The change from baseline and percent change are computed from the total cognitive measurement obtained from the scheduled study visits at weeks 24, 48, and 72. Patients have the option to have the cognitive measures assessed taken at early discontinuation. For early discontinuations, cognitive value will be mapped to the nearest scheduled study visit at week 24, 48, or 72. The planned analyses is an MMRM using an appropriate covariance structure with fixed effects of treatment doses (LY3002813 and placebo), study visit, and interaction between treatment and visit. A baseline covariate adjustment may be used. The primary comparison is between LY3002813 IV doses and placebo for change from baseline or percent. A table of the LSmeans per dose group with associated p-value contrast to placebo will be constructed. A graphical summary of the LSmeans and a mean confidence interval on the y-axis and the study visit on the x-axis for each IV dose-group. Given the small sample size of n=6 patients per IV dose group, simplification of the mixed-effects model might be considered.

In addition to the MMRM analysis, a Bayesian posterior probability may be computed for each LY3002813 dose compared to placebo. For each dose, the credible interval will be computed for each dose relative to placebo. This analysis may be omitted if access to appropriate software such as SAS version 9.4 is not available.

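### The primary SUVr comparison names no week, and the SAP's primary model leaves out the scheduled Week 72 florbetapir scan

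*Protocol*

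**What the plan says.** Protocol 11.2.5.1 plans an MMRM of SUVr with treatment, visit and their interaction. It places the primary comparison of LY3002813 with placebo "for change from baseline in composite SUVr or percent change in composite SUVr at last PET imaging visit". SAP 4.2.5.1 repeats that phrase, and neither document attaches a week to it.

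SAP 4.2.5.1 computes the response from SUVr "obtained from the scheduled study visits at weeks 12, 24, 36, and 48". For scans at early discontinuation it says: "SUVr value will be mapped to the closest scheduled study visit at weeks 12, 24, 36, or 48".

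The scan schedule runs longer. Protocol 7.1 has the primary target engagement outcome "assessed at baseline and at 12 weeks, 24 weeks, 36 weeks, 48 weeks, and 72 weeks after starting treatment", and SAP 3.4 has it "assessed at baseline and 12 weeks, 24 weeks, 36 weeks, 48 weeks, and 72 weeks after starting treatment". Protocol 7.2 relies on the Week 72 scan to judge whether reduction is sustained after Part B dosing. Cohort 3 is the exception: under amendment (f), Protocol 7.1.3 and Attachment 1 end its follow-up at Week 24.

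The SAP does use Week 72 for other outcomes:

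- cognition is "obtained from the scheduled study visits at weeks 24, 48, and 72";
- MRI volumes are "obtained at baseline, 24 weeks, 48 weeks, and 72 weeks as applicable";
- the second tau PET scan is "at Visit 17 approximately 72 weeks post-dose".

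**The concern.** Two problems combine. First, the SAP contradicts itself on the primary outcome: its design summary includes Week 72 and its primary model does not. Because Week 72 is used for cognition, MRI volume and tau PET, the gap is specific to florbetapir SUVr.

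Second, the label for the primary time point is relative. It could mean Week 72, Week 48, each cohort's last scheduled scan, or each patient's last observed scan, and nothing in the documents chooses among them.

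What is at stake is which number answers the sole primary objective. Protocol 7.1 gives the later scans a purpose: sustained reduction in Parts A and B, and maximal removal in Part C. A model ending at Week 48 measures each of these early.

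A relative label also moves with the schedule. On the per-cohort reading, amendment (f) moved Cohort 3's primary week from 72 to 24, on the strength of emerging PET data from Cohorts 1 and 2. Protocol 11.3 has the sponsor's team review PD data as scans accrue, which is a reason to write the week down. It is not a suggestion that anything improper was done.

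**Working it through.** **The plan's own figure.** The Synopsis gives over 90% power for a 17% SUVr reduction with 6 patients per group. No SD, alpha or visit is stated, so the figure cannot be reproduced. Assuming a two-sided 0.05 test and a normal approximation, it needs an SD of at most 17 / ((1.960 + 1.282) × √(2/6)) = 9.1 percentage points. Nothing below depends on it.

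**Step 1. Visit lists.**

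| Source | Post-baseline florbetapir weeks |
|---|---|
| Protocol 7.1; SAP 3.4 | 12, 24, 36, 48, 72 |
| Protocol 7.1.3 and Attachment 1, Cohort 3 | 12, 24 |
| SAP 4.2.5.1, primary MMRM | 12, 24, 36, 48 |
| SAP 4.2.5.1, early-discontinuation mapping | 12, 24, 36, 48 |

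Protocol 9.2.2 allows up to 6 scans and Table AACD.2 counts 4 + 2 = 6. Both fit a baseline scan plus five.

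**Step 2. Scans outside the model.** Planned completers (Protocol 11.1) are 8 in each of Cohorts 1 to 3 (6 LY3002813, 2 placebo) and 12 in each of Cohorts 4 to 7 (9 and 3).

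- Total: 3 × 8 + 4 × 12 = 72, of whom 54 receive LY3002813 and 18 placebo.
- Scheduled for Week 72 (all but Cohort 3): 72 − 8 = 64. LY3002813: 6 + 6 + 4 × 9 = 48 of 54. Placebo: 2 + 2 + 4 × 3 = 16 of 18.
- Scheduled post-baseline scans: 64 × 5 + 8 × 2 = 336.
- Covered by the SAP list: 64 × 4 + 8 × 2 = 272.
- Outside it: 336 − 272 = 64, and 64 / 336 = 19.0%.

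**Step 3. What follows Week 48.**

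- Part B: dosing ends at Week 24, so Week 48 is 24 weeks after dosing and Week 72 is 48 weeks after. Half of the 48-week follow-up is not covered.
- Part C: 19 doses at Weeks 0, 4, …, 72. Those after Week 48 fall at Weeks 52, 56, 60, 64, 68 and 72, which is 6 of 19. In time, 24 of 72 dosing weeks (one third) come after Week 48.

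**Step 4. Early-discontinuation mapping.** The midpoint of Weeks 48 and 72 is Week 60. A scan at Weeks 61 to 71 is nearest to Week 72, but the SAP list sends it to Week 48, which is 61 − 48 = 13 to 71 − 48 = 23 weeks early. A patient who already had the Week 48 scan would then hold two Week 48 values, and no rule says which is used.

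**Step 5. Cohort 3 under a treatment-by-visit model.** Take eight groups (seven cohorts plus pooled placebo), one mean per group and visit, and no Cohort 3 data after Week 24.

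| Visits in model | Cells | Empty (Cohort 3) | Rank | Cohort 3 v placebo at last model week | At Week 24 |
|---|---|---|---|---|---|
| 12, 24, 36, 48, 72 | 40 | 3 | 37 | adding the contrast raises rank to 38: not estimable | rank unchanged: estimable |
| 12, 24, 36, 48 | 32 | 2 | 30 | raises rank to 31: not estimable | rank unchanged: estimable |

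The empty cell is Cohort 3's own, so the result does not depend on how placebo is pooled.

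**The case against.** The Week 48 limit is only in the SAP. Protocol 11.2.5.1 lists no visits, and read against its own schedule the last visit is naturally Week 72, or Week 24 for Cohort 3. The SAP never says in words that the primary comparison is at Week 48. It also plans descriptive SUVr tables across the PET visits, so the Week 72 data may well be reported. The omission could be a drafting slip. Cohort 3's contrast fails only if one late week is imposed on every cohort, and the SAP (December 2015) predates the amendment (December 2017) that shortened that cohort. The mislabelling needs a discontinuation scan after Week 60; such scans are optional and their number is unknown. The Part C figures are schedule maxima, because Protocol 7.1.5 moves patients to placebo after two consecutive scans with SUVr below 1.1. The study is Phase 1b and declares these analyses exploratory.

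Most of this is fair as a limit on the consequences. The Protocol's likely reading is the sensible one, the Cohort 3 mismatch in the SAP is version lag, and the descriptive tables soften the loss. None of it removes the conflict. The Week 48 list and the Week 72 schedule sit in the same SAP version, so version lag does not explain that difference. Descriptive tables do not supply the modelled contrast with placebo. The current Protocol already contains the Cohort 3 change and still gives no week.

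**Conclusion.** The point holds. The primary time point is undefined in both documents. As written, SAP 4.2.5.1 leaves out of the primary model the Week 72 scan that the same SAP schedules: 64 of 336 planned post-baseline scans (19%), from 48 of 54 LY3002813 and 16 of 18 placebo patients. The counts assume planned completer numbers, no dropout and every scheduled scan obtained. For Cohorts 1 and 2, Week 72 rests on Protocol 7.1, 7.1.3 and 9.2.2, because the florbetapir row of their schedule is not column-aligned in the text copy of Attachment 1; its six marks fit five scans plus early discontinuation.

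The Cohort 3 consequence is conditional: no estimable contrast at a common Week 48 or 72, but an estimable one at Week 24. This should be corrected before analysis. It is not a threat to a formal error rate, because none is claimed.

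**What to change.** 1. In SAP 4.2.5.1, add Week 72 to the model's visit list and to the early-discontinuation mapping. State which value is used when the mapped visit already has a scan.
2. In Protocol 11.2.5.1 and SAP 4.2.5.1, define the primary time point as each cohort's last scheduled scan, compared with placebo at the same week: Week 24 for Cohort 3, Week 72 for Cohorts 1, 2 and 4 to 7. State that Cohort 3 has no contrast after Week 24.
3. Also useful: report the Week 24 contrast for all seven cohorts as the common-time comparison, and say which placebo patients enter each contrast. Across the study 18 are planned with a Week 24 scan and 16 with a Week 72 scan; within Part A, 6 and 4.

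The cost is wording. No scan, visit or sample size changes, and the model takes in 336 scheduled scans instead of 272. Protocol 11.2.5 lets the planned analyses change without a protocol amendment, so a SAP revision can carry the correction and the Protocol sentence can be aligned with it. The drawback is more than one named week, none adjusted for multiplicity, with Cohort 3's primary week differing from the others.

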11.2.5.2. Pharmacodynamic Cerebrospinal Fluid Estimation

The CSF results from the LPs taken pre- and postdose will be analyzed to estimate the mean change and percent change from predose. The dependent variables are A β 1-40, A β 1-42, , total tau, and phospho-tau.

11.2.5.3. Cognition and Functional Analyses

ADAS-cog, NTB, MMSE, CDR-SB, ADCS-MCI-ADL, and FCSRT-IR will all be summarized and may be analyzed using an MMRM with preinfusion cognitive measures as a baseline covariate and fixed effects of dose and study visit.

11.2.5.4. Plasma A β

Plasma A β will be analyzed to estimate the mean change from predose. The dependent variables will be A β 1-40 and A β 1-42.

Dosing regimen will be a fixed effect in the model and time may be included as a repeated effect. These analyses are considered exploratory in order to estimate whether there is mean change following doses of LY3002813. If required, a logarithmic transformation may be considered.

11.2.6. Pharmacokinetic/Pharmacodynamic Analyses

Exploratory analyses may be conducted to describe the relationship between serum or CSF exposure and changes in the florbetapir SUV_r, as well as relationships with cognitive endpoints, ADA, AEs, and/or plasma and CSF biomarkers. It is intended that these analyses will be graphical in nature as a function of LY3002813 dose, exposure, and/or time from study entry; however, the relationship may also be described using a modeling approach, if appropriate.

11.2.7. Safety Analyses

11.2.7.1. Clinical Evaluation of Safety

All investigational product and protocol procedure AEs will be listed; if the frequency of events allows, safety data will be summarized using descriptive methodology.

The incidence of symptoms for each treatment will be presented by severity and by association with investigational product, as perceived by the investigator. Symptoms reported to occur

before randomization will be distinguished from those reported as new or increased in severity during the study. Each symptom will be classified by the most suitable term from the medical regulatory dictionary.

The number of investigational product-related SAEs will be reported.

11.2.7.2. Statistical Evaluation of Safety

Safety parameters that will be assessed include safety laboratory parameters, vital signs, and ECG parameters. The parameters will be listed and summarized using standard descriptive statistics. Additional analysis will be performed if warranted upon review of the data.

A shift table for each dose group will be constructed to assess the MRI measurement pre- and postdose for changes and additions of vasogenic edema and microhemorrhages.

Suicide-related thoughts and behaviors based on the C-SSRS will be listed by patient. Only time points and patients that show ideation/behavior of suicide will be displayed (ie, all “no” responses will not be displayed).

Exploratory analyses of Fridericia’s corrected QT interval data from ECG monitoring in a Phase 1 trial are performed to judge the extent and/or risk of QT prolongation. There will be an exploratory assessment of potential prolongation by examining mean change in Fridericia’s corrected QT interval as a function of serum drug concentration obtained and an inspection of the upper confidence limit relative to a value of 10 msec, which is consistent with International Conference on Harmonisation (ICH) guidance. Frequency tables of QTc changes from baseline and large QTc values may also be obtained in accordance with ICH guidance.

